8.4. Secondary Endpoints

The secondary endpoints for this study include the following. For these endpoints, baseline is defined as the last assessment prior to the first dose of study drug.

Efficacy Endpoints:

- Subject-rated pain due to acute back spasm using an NRS (0-10 scale, from no pain to worst possible pain) on Day 4 “right now”.
- Subject rating of medication helpfulness (SRMH; 1-5 scale, from poor to excellent) on Days 4 and 14.
- Subject-rated NRS (0-10 scale) of pain due to acute back spasm on Days 1 to 14; average over the past 12 hours.
- Subject-rated NRS (0-10 scale) of pain due to acute back spasm on Days 1 to 14; average over the past hour.
- Subject-rated NRS (0-10 scale) of average pain due to acute back spasm on rest or movement, rated at the end of the day on Days 1 to 14.
- Time to relief of pain from baseline due to acute back spasm using subject-rated NRS (0-10 scale) on Days 1 to 14.

- Clinician’s Global Impression of Severity (CGI-S) (1–5 scale) at baseline (Day 1).
- Clinician’s Global Impression of Change (CGI-C) 1-7 scale from worse to marked improvement) on Days 4 and 14.
- Patient’s Global Impression of Severity (PGI-S) (1-5 scale) at baseline (Day 1).
- Patient’s Global Impression of Change (PGI-C) based on subject’s global assessment (1-7 scale, from worse to marked improvement) on Days 4 and 14.
- Functionality assessment: fingers to floor distance (FFD) is an index of mobility of the spinal cord and is measured as distance in cm when standing with the spinal cord flexed with complete extension of knee joint, on Days 4 and 14 compared to baseline (Day 1) (assessments should be conducted at the same time of day for all three time points).
- Disability assessment at baseline (Day 1), Day 4, and Day 14:
 - Oswestry Pain and Disability (ODI) questionnaire (10 questions with one answer each for pain intensity, personal care, lifting, walking, sitting, standing, sleeping, sex life [if applicable], social life, and traveling).
- Use of rescue medications (measured daily, assessed as number of rescue tablets administered by the subject via smartphone/use of trial application). Patients are instructed not to take rescue medications on the day of clinic visits on Day 4 and 14.
- Quality of sleep rated by subjects starting at baseline (Day 1) and on Days 2 to 14.
- Visual Analogue Scale (VAS) score for subject-reported sleepiness measured in the clinic on at Day 4.

Safety Endpoints

- Clinical evaluations include:

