11.2. Study Periods

See [Table 2](#) in [Section 29](#) for the schedule of procedures and assessments across the time points for the study.

11.2.1. Clinic Visit 1: Day 1 (Screening/Baseline) and up to Day -3 (Additional Screening Days, If Needed)

Subjects will visit the clinic site for their Screening/Baseline visit (Visit 1, -3 to 0 days) and undergo screening processes for entry into the study. Subjects who meet the inclusion and no exclusion criteria will be entered into the study.

The following screening assessments will be conducted by the Investigator or designee prior to subject enrollment. If needed, the following screening assessments may be completed within 3 days prior to Day 1 (-3 to 0 days):

- Informed consent to be signed
- A urine pregnancy test for all females of childbearing potential
- Medical history and demographic data, including sex, age, race, ethnicity, body weight (kg), height (cm), body mass index (BMI) (kg/m^2), and smoking habits
- Physical examination
- Neurological examination
- The alcohol breathalyzer and urine drug screen
- Laboratory tests (serum chemistry, hematology, and urinalysis)
 - blood sample for DNA genotyping for CYP450 2D6 polymorphism would be collected at same time of other required blood draw
- Vital signs (supine and standing blood pressure [including orthostatic pressure], sitting heart rate (after approximately 3 minutes at rest), respiratory rate, and body temperature,)
- A 12-lead ECG
- Prior and/or concomitant medications during the study will be recorded, as well as those that qualify as rescue medications (see [Section 12.8](#))
- Inclusion/exclusion criteria to be reviewed for qualification of the subject's enrollment into the study

The following baseline assessments will be conducted by the Investigator or designee prior to dosing on Day 1. If any screening assessments were completed prior to Day 1, inclusion/exclusion criteria are to be re-reviewed for qualification of the subject's enrollment into the study:

- Baseline assessments for study efficacy endpoints:
 - Subject rating of pain “right now” (NRS), must be 4 or greater

- Global severity of pain assessment by the physician and the subject on a scale of 1-5, with 1=none, 2=mild, 3=moderate, 4=severe, 5=very severe
- Functionality assessment:
 - Fingers to Floor Distance (FFD)
- Disability assessment:
 - Oswestry Pain and Disability Index (ODI) via the site study-provisioned tablet

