- Deploy subject smartphone/use of trial application to subject
- Quality of sleep via the subject smartphone/use of trial application
- Randomization
- Dispense study drug (for 14 days of dosing) and rescue medication; sufficient for use by subjects for the entire duration of the study
- AEs occurring after the first dose of study medication will be reported. Any concurrent medication use will be recorded.

Subjects will receive all study drug and rescue medication on Day 1. Subjects will begin taking their study drug that same day. Depending on the time of their clinic visit, they should be instructed to begin dosing with either the midday dose (12-2 pm) or the evening dose (6-8 pm).

Subjects will be provided a smartphone/use of trial application on Day 1, just prior to randomization. Subjects will be instructed on how to perform the assessments to be conducted by the subject at home/away from clinic and how to record the results on the smartphone/trial application.

Subjects will be instructed to return to the clinic on Day 4 (Visit 2) and on Day 14 (EOT visit, Visit 3) and to bring all study drug and rescue medication with them as well as smartphone device. Subjects must also return to the clinic for a safety follow-up visit on Day 28 (2-week follow-up visit, Visit 4).

Subjects will be asked and reminded not to consume alcoholic beverages prior to their study visit on Days 1, 4, and 14 and to restrict their consumption during the study duration. At all other times, alcohol consumption is limited to no more than 2 alcoholic drinks or equivalent (beer [24 ounces or 710 mLs], wine [12 ounces or 355 mLs], or distilled spirits [3 ounces or 89 mLs]) per day.

Subjects will be reminded to restrict their consumption of caffeinated beverages to no more than 4 units per day amounts (1 unit =120 mg caffeine or about one eight-ounce cup of coffee).

Subjects will be reminded to refrain from vigorous physical activity, heat and ice packs, and non-pharmacological therapies (e.g., acupuncture, chiropractic adjustment, massage therapy, TENS, physiotherapy) during Days 1 to 14.

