- j Subject rating of pain using NRS due to back spasm, measured daily in the morning 8 to 10 am and in the evening between 8 to 10 pm from Days 1 through 14, for intensity of average pain due to spasm over last 12 hours, and subject rating of average pain over the past 1 hour, all on the subject's smartphone/trial application.
- k Subject rating of average pain using NRS at rest and upon movement at the end of the day (between 8 to 10 pm) on Days 1 to 14 on the subject's smartphone/trial application.
- l Functionality assessments to be administered in the clinic on Days 1, 4 and 14. FFD is measured as distance in cm from the tips of the fingers to the floor when standing with the spinal cord flexed with complete extension of knee joint. This is not captured in an electronic device. Enter score in eCRF.
- m The Oswestry Disability Index (10 sections with one answer each for: pain intensity, personal care, lifting, walking, sitting, standing, sleeping, sex life [if applicable], social life, and traveling) will be captured by study-provisioned tablet ePRO on Days 1, 4, and 14 in the clinic.
- n The use of study-provided rescue medication (acetaminophen 500 mg) taken to control their pain throughout the day will be captured in the subject's smartphone/trial application daily from Day 1 through 14, at the end of the day. Subjects are not to take rescue medications on clinic visits on Days 4 and 14.
- o The subject's quality of sleep will be captured on their smartphone/trial application starting at baseline visit in clinic and on a daily basis at home/away from clinic between 8 to 10 am for Days 1 to 14. In response to the question of "how did you sleep last night", subject responses will be captured on a 5-point scale (from 1=not at all to 5=slept all night).
- p Vital signs include supine and standing blood pressure; heart rate; respiratory rate; and body temperature on Days 1, 4, 14, and 28 (All Visits). Weight and height will be assessed at Visit 1 only.

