SRMH values will be summarized categorically by treatment group for Days 4 and 14 for the ITT Population. The frequency and percentage of subjects in each response category will be presented. The comparison of each group to placebo will be conducted using a Wilcoxon Rank Sum test for the Day 14 values and p-values presented.

7.4.5.5 *Fingers to Floor Distance*

Fingers to floor distance will be assessed at Baseline, Day 4, and Day 14 and will be analyzed using a linear test of trend similar to the primary endpoint on Day 14. Pairwise estimates of the observed value will be presented.

7.4.5.6 *Global Symptom assessments (CGI and PGI)*

Global symptom assessments will be summarized by treatment group for the ITT population. CGI-S and PGI-S will be assessed at the baseline visit only. CGI-C and PGI-C will be assessed at Day 4 and Day 14. The frequency and percentage of subjects in each response category at Baseline, Day 4 and Day 14 will be presented. The comparison of each group to placebo will be conducted using a Wilcoxon Rank Sum test for the Day 14 values and p-values presented.

7.4.5.7 *Quality of Sleep*

Quality of sleep will be analyzed using the same methods described for the global symptom assessments in section 7.4.5.6. The comparison of each group to placebo will be conducted using a Wilcoxon Rank Sum test for the Day 14 observed values.

7.4.5.8 *Time to Pain Relief*

Time to pain relief (days) will be assessed using the NRS assessment of subject rating of pain over the past 12 hours. NRS assessments on or after Day 2 will be considered for time to relief. The first post-baseline occurrence of an AM or PM 12-hour NRS score equal to 2 or lower (0 = no pain, 10 = worst possible pain) will be used as the criterion for relief.

Subjects who withdraw from the study prior to the end of treatment visit or who complete the treatment period without having met the criteria for relief will be censored at the time of their last NRS assessment. Time to relief will be presented in days as (date of relief/censoring – date of first dose + 1).

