Observed ODI score and change from baseline will be summarized descriptively for each treatment group for the ITT population. Each dose group will be compared to placebo using an ANCOVA model with observed value as the response, main effects for treatment group and a covariate adjusted for the baseline ODI score. The LSM, LSMD, 95% CI and p-values will be presented at Day 14.

Individual section scores will be summarized separately for the ITT population by treatment group. The frequency and percentage of subjects in each response category at Baseline, Day 4 and Day 14 will be presented. The comparison of each group to placebo will be conducted using a Wilcoxon Rank Sum test for the Day 14 values and p-values presented.

7.4.5.11 *Visual Analogue Scale of Sleepiness*

The Day 4 VAS ratings of sleepiness will be summarized descriptively by treatment group for the ITT population. Each dose group will be compared to placebo using an ANOVA model with the observed values as the response and main effects for treatment group. The LSM, LSMD, 95% CI and p-values will be presented.

7.4.5.12 *Daily Activities*

Daily activity scores will be summarized categorically for Days 1 to 14 by treatment group for the ITT population. The frequency and percentage of subjects in each response category will be presented. The comparison of each group to placebo will be conducted using a Wilcoxon Rank Sum test for the Day 14 values and p-values presented.

7.4.6 *Statistical/Analytical Issues*

7.4.6.1 *Adjustments for Covariates*

The MMRM model to test for linear trend for the primary endpoint will include a covariate adjustment for the baseline value. Secondary endpoints utilizing an MMRM will be analyzed similarly when a baseline value is captured.

7.4.6.2 *Handling of Dropouts or Missing Data*

Primary and secondary endpoints including all NRS assessments (right now, past 12 hours, past 1 hour, at rest, on movement), Fingers to floor Distance, Clinician's Global Impression, and Oswestry Disability Index assessments will be analyzed using both observed data and data imputed using last observation carried forward (LOCF), if the dropout rate is $\geq 5\%$ (20/400 subjects). In the LOCF method, the most recent non-missing value for the endpoint is carried forward to replace a missing value at a post-baseline visit within a subject. Baseline values will not be carried forward.

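### Sleep quality has a pre-dose rating that the Day 14 Wilcoxon test does not use; the test is valid, and adjusting for baseline would add some power if baseline and Day 14 ratings are correlated

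*SAP*

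**What the plan says.** **A baseline exists.** Protocol 8.4 lists the endpoint as "Quality of sleep rated by subjects starting at baseline (Day 1) and on Days 2 to 14". Protocol 11.2.1 introduces the Day 1 list with "The following baseline assessments will be conducted by the Investigator or designee prior to dosing on Day 1". That list includes "Quality of sleep via the subject smartphone/use of trial application", placed ahead of the randomization item. The schedule footnote in SAP 6.2 has the rating collected "starting at baseline visit in clinic and on a daily basis at home/away from clinic between 8 to 10 am for Days 1 to 14". The item asks about the previous night on a five-point scale. SAP 7.1.3 takes as baseline the last value before the first dose.

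**The test does not use it.** SAP 7.4.5.7 applies the method of the global symptom assessments (7.4.5.6) and then specifies: "The comparison of each group to placebo will be conducted using a Wilcoxon Rank Sum test for the Day 14 observed values". Protocol 17.4.2.2 also assigns sleep quality to the global-assessment method. Under that method the baseline can appear only in a frequency table.

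**The covariate rule does not reach it.** SAP 7.4.6.1 extends baseline adjustment to secondary endpoints that are analyzed by MMRM. Sleep quality is not one of them. It is also absent from the LOCF list (7.4.6.2) and the per-protocol list (7.4.6.6), so no other planned analysis of sleep uses the baseline.

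**The concern.** The method was written for a different kind of scale. The SAP says "CGI-C and PGI-C will be assessed at Day 4 and Day 14". Those two are change ratings with no baseline of their own, so an unadjusted rank test is the natural choice for them. Sleep quality is a status score measured the same way before and after treatment.

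Elsewhere the SAP uses a baseline where it has one: in the primary model (7.4.4) and in the ANCOVA for the ODI total (7.4.5.10). Its one stated reason for dropping a baseline covariate is that none is collected for VAS sleepiness (7.7.1). That reason does not apply to sleep quality.

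At stake is the power of four dose-versus-placebo comparisons on a secondary efficacy endpoint in a dose-ranging trial. If baseline and Day 14 ratings are correlated, part of the Day 14 variation could be removed with data the trial already collects.

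**Working it through.** **Inputs from the documents.** 80 per arm and effect sizes of 0.35, 0.40 and 0.45 (Protocol 17.2, Table 1, planned for the pain NRS); two-sided 5% level (Protocol 17.1, SAP 7.1.1); five ordered categories (SAP 6.2).

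**Assumed, because the documents give no figure.** The effect on sleep, taken here from the pain planning, and the correlation ρ between baseline and Day 14 ratings, varied from 0 to 0.6.

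**1. Reproduce the plan's own figure.** Power for one dose against placebo is Φ(d·√(n/2) − 1.96). With n = 80 and d = 0.40: 0.40 × √40 = 2.530, and Φ(0.570) = 71.6%. Table 1 gives 71%. For d = 0.35 and 0.45 the formula gives 60.0% and 81.2%, against 60% and 81%. The plan states no power for sleep quality.

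**2. Upper guide, treating the scale as continuous.** Adjustment multiplies the residual variance by 1 − ρ², so power becomes Φ(d·√(n/2)/√(1 − ρ²) − 1.96). At d = 0.40:

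| ρ | 1 − ρ² | 80 per arm acts like (80/(1 − ρ²)) | power | gain over 71.6% |
|---|---|---|---|---|
| 0.2 | 0.96 | 83.3 | 73.3% | 1.7 |
| 0.3 | 0.91 | 87.9 | 75.6% | 4.0 |
| 0.4 | 0.84 | 95.2 | 78.8% | 7.2 |
| 0.5 | 0.75 | 106.7 | 83.2% | 11.6 |

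Five coarse categories weaken both the effect and the correlation, so the ordinal gain should be smaller.

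**3. Ordinal simulation at 0.45 SD.** Bivariate normal latent scores were cut into five categories (baseline at −1.2, −0.3, 0.5, 1.3; Day 14 at −1.6, −0.8, 0, 0.9). There were 80 per arm and 20,000 trials per setting. The rank-sum comparison was set against the same comparison after regressing Day 14 ranks on baseline ranks.

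| latent ρ | rank-sum power | rank-ANCOVA power | gain | type I error, rank-sum / rank-ANCOVA |
|---|---|---|---|---|
| 0 | 75.48% | 75.18% | −0.30 | 5.00% / 4.99% |
| 0.2 | 74.92% | 76.21% | +1.29 | 5.02% / 5.06% |
| 0.3 | 74.88% | 77.65% | +2.77 | 5.32% / 5.08% |
| 0.5 | 75.84% | 84.05% | +8.21 | 5.01% / 5.19% |
| 0.6 | 75.60% | 88.20% | +12.60 | 5.02% / 4.96% |

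The Monte Carlo standard error of one power is about √(0.75 × 0.25/20000) = 0.3 points. With the effect present, the mean rank correlation was 0.173, 0.260 and 0.436 at latent ρ of 0.2, 0.3 and 0.5. That explains the smaller gains than in step 2.

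**4. The same comparison at 0.4 SD**, the middle of the plan's range, with 4,000 trials per setting. Rank-ANCOVA gained about 1 point at ρ = 0.2, 2 to 3 at 0.3, 4 to 6 at 0.4 and 7 to 9 at 0.5. It cost under half a point at ρ = 0, and type I error stayed near 5%. The lower ends apply when Day 14 ratings pile up in the top category, as recovery may produce.

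**The case against.** The strongest reply is that nothing here is an error. The SAP follows the protocol's method for sleep, the Wilcoxon test suits an ordinal scale, and its type I error is correct. All of that stands.

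The gain may also be small. The item rates a single night, not habitual sleep. Baseline is a night during an acute spasm that began within 7 days, with pain of at least 4 (Protocol 9.1). Day 14 is a night after two weeks of treatment. A low correlation is quite possible, and at 0.2 the gain is about 1 point. This also stands, and it is why the size must be given as a range. Against it, adjustment costs under half a point even at zero correlation.

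Sleep quality appears in none of the stated objectives, and SAP 7.4.6.5 makes no multiplicity adjustment, so no stated decision turns on this test. That limits the importance but not the logic.

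A reader might infer more from the omission, in three ways that the documents do not support:
- **That the comparison is biased, or exposed to chance baseline imbalance.** Randomization protects it, and chance imbalance is already allowed for in the error rate of a valid test.
- **That precision is certainly lost to a material degree.** That needs a correlation that the documents do not give.
- **That the ten ODI section scores share the same fault.** They too get an unadjusted Day 14 rank test ("The comparison of each group to placebo will be conducted using a Wilcoxon Rank Sum test for the Day 14 values and p-values presented"), but they are a breakdown of a total that SAP 7.4.5.10 already adjusts for baseline. They score 0 to 5, so the five-category figures above do not cover them.

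**Conclusion.** The point holds as an optional efficiency improvement. A pre-dose sleep rating is collected and the planned Day 14 comparison does not use it, but that comparison is valid as written.

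Under a borrowed effect of 0.4 SD and 80 per arm, the gain is negligible at correlations up to 0.2 and modest at 0.3. It is worth having at 0.4 to 0.5, at up to about 9 points. Both the effect and the correlation are assumptions. The figure of 80 per arm is the planned number; SAP 7.7.2 removes one site's data, so the analyzed number may be lower. The case for the change is that its downside is very small, not that a large loss has been shown.

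**What to change.** Before unblinding, amend SAP 7.4.5.7 as follows:

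- **Main comparison.** For each dose against placebo, use a rank-ANCOVA of the Day 14 rating on the baseline rating, with baseline as defined in 7.1.3. Name this one method. A van Elteren test stratified by baseline category is the obvious alternative, but in simulation it gained nothing at a correlation of 0.2 and lost 1 to 2 points at zero.
- **Supportive.** Keep the plain Wilcoxon test on all subjects with an observed Day 14 rating. This also covers subjects with no baseline entry, who would drop out of the adjusted test.
- **Record.** Enter the change in 7.7.1, since the protocol also specifies the Wilcoxon method.

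Leave CGI-C, PGI-C and SRMH as they are. Extending the change to the ODI sections is optional. The cost is a short SAP edit and a few lines of code; no new data are needed.

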8.2. Secondary Objectives

The secondary objectives of this study are:

- To assess the safety and tolerability of tolperisone in subjects with pain due to acute back spasm.
- To determine the onset of action of tolperisone in treatment of pain due to acute back spasm.
- To determine the duration of pain relief of tolperisone in treatment of pain due to acute back spasm.
- To determine the need for rescue medication when treated with various doses of tolperisone for pain due to acute back spasm.

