17.4.2.2. Secondary Efficacy Analyses

The analysis performed for the primary endpoint will be repeated for the NRS at Day 4.

In addition to the primary efficacy analysis, subjects will also use the NRS scale to record pain intensity due to back spasm each day on an outpatient basis. Ratings will be averaged for both morning and evening recordings on Days 1 through Day 14 and summarized by dose level and day using descriptive statistics. Mean NRS pain intensity scores will also be plotted in a line graph over time, with associated standard errors (SEs) for Days 1 through 14. The analysis will be repeated using the evening values only for NRS scores on rest and also on movement. The comparison of each group to placebo will be conducted using a mixed effects model as described for the primary analysis.

The SRMH and the Functionality Assessment: FFD will be analyzed using the same methods described for the primary endpoint.

Global symptom assessments (CGI and PGI) will be summarized by the percentage of subjects reporting each individual response. The proportion of subjects in each category will be recorded at each day. The comparison of each group to placebo will be conducted using a Wilcoxon Rank Sum test.

Quality of sleep will be analyzed using the same methods described for the global symptom assessments.

Median time (in hours) to relief of pain on Days 1 and 14 compared to baseline will be plotted using Kaplan-Meier (K-M) curves. Estimates of the median times will be presented along with

their associated 95% confidence interval (CI) in a corresponding table. Treatment group comparisons will be summarized with hazard ratios and their associated 95% CI from a Cox Proportional Hazards regression model with treatment as the main effect and p-values from the generalized Wilcoxon test.

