5.2 Secondary Study Objective

The secondary objectives of this study are to:

- Assess the safety and tolerability of tolperisone in subjects with pain due to acute back spasm;
- Determine the onset of action of tolperisone in treatment of pain due to acute back spasm;
- Determine the duration of pain relief of tolperisone in treatment of pain due to acute back spasm; and
- Determine the need for rescue medication when treated with various doses of tolperisone for pain due to acute back spasm.

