6.4.1.2 Secondary Efficacy Variables

Secondary efficacy endpoints include assessments administered on a study-provisioned tablet at the clinical site on Day 1 (baseline), Day 4, and Day 14 or captured by the subject with smartphone/trial application daily at home from Day 1 to Day 14 (See Table 2)

- Subject-rated pain due to acute back spasm “right now” using NRS on Day 4
- Subject-rated average pain due to acute back spasm over past 12 hours using NRS on Days 1 to 14, measured in morning and evening.
- Subject-rated average pain due to acute back spasm over past 1 hour using NRS on Days 1 to 14, measured in morning and evening
- Subject-rated average pain at rest due to acute back spasm using NRS on Days 1 to 14, measured in evening
- Subject-rated average pain on movement due to acute back spasm using NRS on Days 1 to 14, measured in evening
- Subject rating of medication helpfulness (SRMH) using a scale of 1-5 on Days 4 and 14, where 1=poor, 2=fair, 3=good, 4=very good, and 5=excellent.
- Time to relief of pain due to acute back spasm (days) from baseline using subject-rated NRS of pain over past 12 hours. The first NRS score of 2 or lower will be used to define relief.
- Clinician’s Global Impression of Severity (CGI-S) using 1–5 scale at baseline (Day 1), where 1=no pain, 2=mild pain, 3=moderate pain, 4=severe pain, and 5=worst possible pain
- Clinician’s Global Impression of Change (CGI-C) using a scale of 1-7 on Days 4 and 14, where 1=Very Much Worse, 2=Much Worse, 3=Minimally Worse, 4=No Change, 5=Minimally Improved, 6=Much Improved, and 7=Very Much Improved

- Patient's Global Impression of Severity (PGI-S) using a scale of 1–5 scale at baseline (Day 1), where 1=no pain, 2=mild pain, 3=moderate pain, 4=severe pain, and 5=worst possible pain
- Patient's Global Impression of Change (PGI-C) based on subject's global assessment using a scale of 1-7 on Days 4 and 14, where 1=Very Much Worse, 2=Much Worse, 3=Minimally Worse, 4=No Change, 5=Minimally Improved, 6=Much Improved, and 7=Very Much Improved).
- Fingers to floor distance (FFD) measured at Baseline (Day 1), Day 4, and Day 14

FFD is an index of mobility of the spinal cord and is measured as distance in cm when standing with the spinal cord flexed with complete extension of knee joint, on Days 4 and 14 compared to baseline (Day 1) (assessments should be conducted at the same time of day for all three time points).

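### Time to pain relief is counted in whole calendar days from Day 2, where the protocol specifies hours over Days 1 to 14, and the SAP neither lists nor explains the change

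*SAP*

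**What the plan says.** **Protocol.** Section 8.4 defines the endpoint as "Time to relief of pain from baseline due to acute back spasm using subject-rated NRS (0-10 scale) on Days 1 to 14". Section 17.4.2.2 gives the unit: "Median time (in hours) to relief of pain on Days 1 and 14 compared to baseline will be plotted". Section 8.2 lists the related secondary objective: "To determine the onset of action of tolperisone in treatment of pain due to acute back spasm". SAP 5.2 repeats that objective.

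**SAP.** Section 6.4.1.2 changes the unit and fixes the recall period: "Time to relief of pain due to acute back spasm (days) from baseline using subject-rated NRS of pain over past 12 hours". Section 7.4.5.8 sets the rest:
- Eligible ratings: "NRS assessments on or after Day 2 will be considered for time to relief".
- Event: "The first post-baseline occurrence of an AM or PM 12-hour NRS score equal to 2 or lower".
- Derivation: "Time to relief will be presented in days as (date of relief/censoring – date of first dose + 1", in brackets in the original.

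Groups are then compared by Kaplan-Meier medians, a Cox model and a generalized Wilcoxon test.

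**Disclosure.** SAP section 4 undertakes to explain any change from the protocol's statistical methods. Section 7.7.1 lists three: the sleepiness VAS, the daily activity scores and the medication-helpfulness rating. Time to relief is not among them. The Day 2 start is also absent from the SAP's own definition in 6.4.1.2. It also sits awkwardly with 7.1.2, which says statistical analyses of the daily app data use Days 1 through 14.

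**The concern.** An endpoint meant to inform onset of action needs to separate early responders from later ones. The SAP lets a morning or an evening score establish relief, then keeps only the date, so the information on which of the two did so is thrown away. It also removes the only post-dose diary rating scheduled on Day 1 for a midday or evening start. If doses differ in how fast they act, part of that difference could lie in the interval that the coding merges. The generalized Wilcoxon test gives more weight to early event times, and those are the ones most affected. Separately, a reader of the study report would find days where the protocol promised hours, with no explanation.

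**Working it through.** The documents give no event count, median or power for this endpoint, so there is no plan figure to reproduce. The check is interval arithmetic on the stated windows.

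**Inputs**
- First dose on Day 1: 12-2 pm or 6-8 pm (Protocol 10.1 and 11.2.1).
- Ratings: 8-10 am and 8-10 pm, for both the 12-hour and the 1-hour recall (Protocol Table 2, footnote j).
- SAP value = date of relief - date of first dose + 1, with ratings eligible from Day 2 (SAP 7.4.5.8).

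**Formula.** In clock hours from midnight on Day 1, the shortest elapsed time is the start of the rating window minus the end of the dose window. The longest is the end of the rating window minus the start of the dose window.

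| Rating | Midday start (12-14 h) | Evening start (18-20 h) | SAP value |
|---|---|---|---|
| Day 1 PM (20-22 h) | 20-14 = 6 to 22-12 = 10 h | 20-20 = 0 to 22-18 = 4 h | not eligible |
| Day 2 AM (32-34 h) | 32-14 = 18 to 34-12 = 22 h | 32-20 = 12 to 34-18 = 16 h | 2 |
| Day 2 PM (44-46 h) | 44-14 = 30 to 46-12 = 34 h | 44-20 = 24 to 46-18 = 28 h | 2 |

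The 0 h bound comes from the windows alone. The app reminder to dose at least 1 hour before the rating (Protocol 13.1) would raise it to about 1 h if followed.

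**What follows**
1. The smallest attainable value is 2 - 1 + 1 = 2. It is a label for 12 to 34 h, not 48 h elapsed. SAP Table 4 also provides for a first dose between midnight and noon; the upper end then becomes 46 - 0 = 46 h.
2. For a given start slot, Day 2 AM and Day 2 PM are at least 8 h apart (30-22 for midday, 24-16 for evening), yet they are tied.
3. The same happens every day. Relief can take 13 values (2 to 14), against 13 × 2 = 26 rating occasions from Day 2, or 27 with the Day 1 evening.
4. For midday and evening starts the coding ties subjects but does not reverse them. The latest time coded 2 is 34 h, and the earliest coded 3 is Day 3 AM after an evening start, 56-20 = 36 h. A reversal is possible only with a morning start (up to 46 h coded 2).
5. A subject relieved on Day 1 is recorded as 2 if the Day 2 score also qualifies, and otherwise later or censored.
6. For midday and evening starts, the Day 1 evening rating comes at most 10 h after first dose, so its 12-hour recall always reaches back before dosing. The Day 2 morning rating comes at least 12 h after, so its recall does not. This is a plausible reason for the Day 2 start, but the SAP does not give it.

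**The case against.** The strongest case for the SAP has four parts.

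- **Day 2 suits the 12-hour recall.** Step 6 above bears this out. It supports excluding Day 1 for this rating. It does not support merging morning with evening, or leaving the exclusion unexplained.
- **The protocol is not a clean standard.** Its one sentence on hours refers to Days 1 and 14, which is unclear, and it fixes neither a recall period nor a relief threshold. So the 12-hour recall and the cut-off of 2 are not departures. The unit and the Day 1 window are.
- **Hours can suggest more precision than exists.** Ratings about 12 h apart leave relief interval-censored, and the same Day 2 morning rating is 12-16 h or 18-22 h depending only on the first-dose slot. This stands as a limit on interpretation.
- **No effect on the comparison is shown.** Rank-based methods lose only ties, and the documents do not say how many subjects would fall from a baseline of 4 or more to 2 or lower so early. This stands too: the loss is of resolution, of unknown effect on any p-value.

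A reader might infer that no early effect can be seen at all, or that onset is addressed nowhere else. The documents do not support that. SAP 7.4.5.2 summarises morning and evening 1-hour and 12-hour ratings by study day and plots the daily averages, Day 1 included, and SAP 7.4.5.1 tests right-now pain at Day 4.

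A reader might also conclude that the past-1-hour rating with Day 1 should become the main definition. That is a trade-off, not a correction. The 1-hour rating is noisier, and SAP 7.5.5.5 says analgesic use was allowed on Day 1, so a low score that evening may reflect another drug.

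**Conclusion.** The point holds as an undisclosed change of definition that discards resolution already collected. Relief first shown 12 to 34 h after first dose is recorded as one value, the Day 1 evening rating is not used, and 7.7.1 is silent on both. The consequence falls on the only planned between-group time-to-event test aimed at the onset objective.

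The size rests on the stated dose and rating windows being followed. It is a statement about resolution and ties. The documents do not show that doses differ in the first day and a half, so no loss of power can be quantified. The endpoint is secondary in a Phase 2 study without multiplicity adjustment, and neither the primary analysis nor the sample size is touched. The change is still worth making because it costs almost nothing.

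**What to change.** **Main definition.** Derive time to relief in hours, from the recorded date and time of first dose to the morning or evening diary point at which the 12-hour NRS is first 2 or lower. Use the diary time stamp, or the window midpoint (9 am or 9 pm) if none is stored. Censor at the last 12-hour rating on the same scale. Add a rule for a missing first-dose time; SAP 7.4.3 has one only for the last dose.

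**Disclosure.** Align 6.4.1.2 with 7.4.5.8. In 7.7.1, list and justify the unit used and the exclusion of Day 1.

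**Supplementary analysis.** Repeat with the past-1-hour NRS, admitting Day 1 evening ratings taken at least 1 hour after first dose. State that it is noisier and that analgesics were allowed on Day 1.

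**Reporting.** Say that times are interval-censored at about 12 h, so medians in hours do not give an exact onset.

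**Cost.** SAP wording and derivation code, settled before unblinding. Both ratings are already collected, and SAP Table 4 already relies on the time of first dose. Whether diary time stamps are stored is not stated, hence the midpoint rule.
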